### 6.2. General Data Handling Conventions

For the laboratory safety variables and biomarker data, if the data are below the lower limit of quantification (LLOQ) / limit of linearity, half of the lower limit value (i.e., LLOQ/2) will be used for quantitative analyses. For data above the upper limit of quantification (ULOQ) / limit of linearity, the upper limit value (i.e., ULOQ) will be used for quantitative analyses.

### 6.3. Data Handling Convention for Missing Data

Missing data will not be imputed in listings. This section includes the methods for missing data imputation for some summary analyses, if necessary.

#### *Adverse event*

If the intensity of a TEAE is missing, it will be classified as “severe” in the frequency tables by intensity of TEAE. If the assessment of relationship of a TEAE to the study drug is missing, it will be classified as “related” in the frequency tables by relation to the study drug.

#### **Adverse event start date**

AE start date will be used for AE classification and analysis of AESIs. If AE start date is not complete, then the character variable will keep the original incomplete date, the numerical date variable will be imputed and an imputation flag will indicate which date component is missing.

If AE start day is missing, and AE start month and year are not missing: If AE start year is the same as first dose year and the AE start month is the same as the first dose month, then impute AE start day using the day of first dose. If this leads to a date after the AE end date, use AE end date

instead. Otherwise impute the AE start day using the first day of the month. If this leads to a date before informed consent, the informed consent date will be used. Imputation flag is 'D'.

If AE start month is missing, and AE start year is not missing: If AE start year is less than the first dose year, use the informed consent day and month. If AE start year is equal to the first dose year, use the first dose day and month. If this leads to a date after the AE end date, use AE end date instead. If AE start year is after the first dose year, use 01 January. Imputation flag is 'M'.

If AE start year is missing: Impute AE start date using the day of first dose. If this leads to a date after the AE end date, use AE end date instead. Imputation flag is 'Y'.

#### Adverse event end date

The general recommendation is not to impute AE end date. However, since AE end date will be used for the imputation of AE start date, in order to carry through the logic for programming, the following intermediate step will be used. Afterwards, only the original character/numeric date recorded in CRF will be kept in the final analysis dataset.

If AE end day is missing, and AE end month and year are not missing: Impute AE end date using the last day of the month. If this leads to a date after end of study follow up date, use the end of study date instead.

If AE end month is missing, and AE end year is not missing: Impute AE end date using 31 December as the day and month. If this leads to a date after end of study follow up date, use the end of study date instead.

If AE end year is missing: Impute AE end date using the end of study date.

#### ***Medication start and end date missing***

To determine whether a medication is pre-treatment medication or concomitant medication or both, the missing medication start date is estimated as early as possible, and the missing medication end date is estimated as late as possible. If the medication start date is missing, the onset day will not be calculated in medication listings.

#### Prior medication start date

If start day is missing, and start month and year are not missing: Impute the start day using the first day of the month. Imputation flag is 'D';

If start month is missing, and start year is not missing: Impute the day and month using 01 January. Imputation flag is 'M'.

If start year is missing: Impute start date using 2 years before informed consent date. Imputation flag is 'Y'.

A special note: for start date with year missing, the general principle is not to impute. However, in order to simplify the programming flow, the imputation is proposed to align with the protocol which specifies to collect up to 2 years prior medication. Since the start date of prior medication will not be used in any analysis, the rule will not impact the analysis result.

#### Prior medication end date

If end day is missing, and end month and year are not missing: Impute end date using the last day of the month. If this leads to a date on or after first dose intake date, use first dose intake date -1 instead. Imputation flag is 'D'.

If end month is missing, and end year is not missing: Impute end date using 31 December as the day and month. If this leads to a date on or after first dose intake date, use first dose intake date -1 instead. Imputation flag is 'M'

If end year is missing: Impute end date using the first dose intake date -1. Imputation flag is 'Y'.

#### Concomitant medication start date

The imputation rule for concomitant medication start date is the same as AE start date.

#### Concomitant medication end date

If end day is missing, and end month and year are not missing: Impute end date using the last day of the month. If this leads to a date after end of study follow up date, use the last visit study date instead. Imputation flag is 'D'.

If end month is missing, and end year is not missing: Impute end date using 31 December as the day and month. If this leads to a date after end of study follow up date, use the last study visit date instead. Imputation flag is 'M'.

If end year is missing: Impute date using the end of last study visit date. Imputation flag is 'Y'.

#### Medication coding

Medications whose ATC level 4 cannot be coded will be summarized by setting ATC4=ATC2 in the table programs. However, these uncoded ATC level 4 records still need to be confirmed with study DM and study MD.

#### ***PCSV***

Patients who had post-baseline PCSV but missing baseline value will be regarded as having treatment emergent PCSV.

### **6.4. Analysis Visit Windows**

Data analyzed by-visit-analysis (efficacy [excluding daily diary data], laboratory data, vital sign, ECG, ADA) will be summarized by the study scheduled visits described in study protocol and SAP Section 11.2, "Schedule of Event".

The analysis visit windows will be created per study schedule of events (SOE) table for each parameter and will be applied if the data from the study scheduled visits are unavailable. The following general rules will be applied to unscheduled visit and/or early termination (ET) visit mapping for each parameter:

1. If ET visit falls in an analysis window which has no missing value of this parameter, ET will be mapped to the next scheduled visit.
2. If both ET visit and unscheduled visit of the same parameter are available in the same analysis visit window, only ET visit will be mapped.

3. If multiple unscheduled visits of the same parameter are available in the same analysis visit window, the unscheduled visits will be mapped using the following rules:
  - a. The closest unscheduled visit from the target day will be selected.
  - b. If multiple unscheduled visits exist on the same day, the first unscheduled visit will be used.
4. If mapping distance is greater than 4 weeks, the unscheduled visit will not be mapped.

Unscheduled visits and early termination (ET) visit will be mapped per the analysis visit windows for Part B and Part C (Table 1-5) based on the study day/visit of each parameter, respectively.

Due to COVID-19 pandemic, patients may have delayed week 24 visit and week 52 visit. The two visits will not be remapped for primary analysis of efficacy.

**Part B (data collected after the first injection in Part C will not be used for Part B analysis)**

**Table 1: Analysis Visit Window for Efficacy Endpoints in Part B**

Visit from SOE	Target Study Day in Part B a	Analysis Visit Window based on Study Day in Part B		
		Histology endpoints, Transcriptome endpoints, EREFS, EndoFLIP endpoints	PGIC, PGIS	EOE-IQ, EoE-SQ, TNSS, RQLQ(S)+12, ACQ-5, POEM
Baseline	1	≤1	≤1	≤1
Week 12	85		[2, 113]	[2, 127]
Week 20	141		[114, 155]	
Week 24 (Part B end of treatment)	169	[2, 190] Error! Reference source not found.	[156, 190] Error! Reference source not found.	[128, 190] Error! Reference source not found.
Week 28 c (Extended period of Part B)	197	[191, 204]		
Week 30 c (Extended period of Part B)	211	[205, 218]		
Week 32 c (Extended period of Part B)	225	[219, 232]		
Week 34 c (Extended period of Part B)	239	[233, 246]		
Week 36 c (Extended period of Part B)	253	≥247		

**Error! Reference source not found.** Study days are calculated from the day of 1st injection of Part B. Study day = (date of assessment – 1st injection date +1) when date of assessment ≥ 1st injection date; otherwise study day = (date of assessment – 1st injection date). If patient never received any dose of study drug, randomization date will be used in place of 1st injection date.

**Error! Reference source not found.** If unscheduled or ET visit occurs in this window and it is after the first dose of Part C, it will be considered for Week 26 in Part C.

c Those are dummy analysis visit windows for patients with extended dosing in Part B. ET or unscheduled visit occurred after week 24 visit and before first dose of part C will be mapped per Table 5.

**Table 2: Analysis Visit Window for Safety and Biomarkers in Part B**

Visit from SOE	Target Study Day in Part B a	Analysis Window based on Study Day in Part B					
		Vital signs	Weight	Physical examination, ECG, Height	Laboratory, PK, ADA	Eotaxin-3, Total IgE, Allergen-specific IgE, IgG4	TARC
Baseline	1	≤1	≤1	≤1	≤1	≤1	≤1
Week 1	8	[2, 11]					
Week 2	15	[12, 22]	[2, 22]				
Week 4	29	[23, 43]	[23, 43]			[2, 57]	[2, 89]
Week 8	57	[44, 71]	[44, 71]				
Week 12	85	[72, 99]	[72, 99]		[2, 113]	[58, 127]	
Week 16	113	[100, 127]	[100, 127]				
Week 20	141	[128, 155]	[128, 155]		[114, 155]		
Week 24 (Part B end of treatment)	169	[156, 190] Error! Reference source not found.	[156, 190] Error! Reference source not found.	[2, 190] Error! Reference source not found.	[156, 190] Error! Reference source not found.	[128, 190] Error! Reference source not found.	[90, 190] Error! Reference source not found.
Week 28 c (Extended period of Part B)	197	[191, 204]					
Week 30 c (Extended period of Part B)	211	[205, 218]					
Week 32 c (Extended period of Part B)	225	[219, 232]					
Week 34 c (Extended period of Part B)	239	[233, 246]					
Week 36 c (Extended period of Part B)	253	≥247					

a **Error! Reference source not found.** Study days are calculated from the day of 1st injection of Part B. Study day = (date of assessment – 1st injection date +1) when date of assessment ≥ 1st injection date; otherwise study day = (date of assessment – 1st injection date). If patient never received any dose of study drug, randomization date will be used in place of 1st injection date.

b **Error! Reference source not found.** If unscheduled or ET visit occurs in this window and it is after the first dose of Part C, it will be considered for Week 26.

c Those are dummy analysis visits windows for patients with extended dosing in Part B. ET or unscheduled visit occurred after week 24 visit and before first dose of part C will be mapped per Table 5.

**Part C (only applies to patients who received at least 1 dose of Part C study drug)**

**Table 3: Analysis Visit Window for Efficacy Endpoints in Part C**

Visit from SOE	Target Study Day in Part C a	Analysis Window based on Study Day in Part C	
		Histology endpoints, Transcriptome endpoints, EREFS, EndoFLIP endpoints	PRO endpoints
Baseline of Part C	1	≤1	≤1
Week 36	85		[2, 141]
Week 52 (Part C end of treatment)	197	[2, 218]	[142, 218]
Week 56 b (Extended period of Part C)	225		[219, 232]
Week 58 b (Extended period of Part C)	239		[233, 246]

Visit from SOE	Target Study Day in Part C a	Analysis Window based on Study Day in Part C	
		Histology endpoints, Transcriptome endpoints, EREFS, EndoFLIP endpoints	PRO endpoints
Week 60 b (Extended period of Part C)	253	[247, 260]	
Week 62 b (Extended period of Part C)	267	[261, 274]	
Week 64 b (Extended period of Part C)	281	>=275	

**Error! Reference source not found.** Study days are calculated from the day of 1st injection of Part C. Study day = (date of assessment – 1st injection date +1) when date of assessment ≥ 1st injection date; otherwise study day = (date of assessment – 1st injection date). If patient never received any dose of study drug, randomization date will be used in place of 1st injection date.

b Those are dummy analysis visits windows for patients with extended dosing in Part C. ET or unscheduled visit occurred after week 52 visit will be mapped per Table 5.

**Table 4: Analysis Visit Window for Safety and Biomarkers in Part C**

Visit from SOE	Target Study Day in Part C a	Analysis Window based on Study Day in Part C					
		Vital Signs	Weight	Physical examination, ECG, Height, TARC	Laboratory	PK, ADA	Eotaxin-3, Total IgE, Allergen-specific IgE, IgG4
Baseline of Part C	1	≤1	≤1	≤1	≤1	≤1	≤1
Week 26	15	[2, 22]	[2, 22]				[2, 36]
Week 28	29	[23, 43]	[23, 43]				
Week 32	57	[44, 71]	[44, 71]			[2, 127]	[37, 127]
Week 36	85	[72, 99]	[72, 141]		[2, 141]		
Week 40	113	[100, 127]					
Week 44	141	[128, 155]					
Week 48	169	[156, 183]					
Week 52 (Part C end of treatment)	197	[184, 218]	[142, 218]	[2, 218]	[142, 218]	[128, 218]	[128, 218]
Week 56 b (Extended period of Part C)	225	[219, 232]					
Week 58 b (Extended period of Part C)	239	[233, 246]					
Week 60 b (Extended period of Part C)	253	[247, 260]					
Week 62 b (Extended period of Part C)	267	[261, 274]					
Week 64 b (Extended period of Part C)	281	>=275					

**Error! Reference source not found.** Study days are calculated from the day of 1st injection of Part C. Study day = (date of assessment – 1st injection date +1) when date of assessment ≥ 1st injection date; otherwise study day = (date of assessment – 1st injection date). If patient never received any dose of study drug, randomization date will be used in place of 1st injection date.

b Those are dummy analysis visits windows for patients with extended dosing in Part C. ET or unscheduled visit occurred after week 52 visit will be mapped per Table 5.

**12-week follow-up period after Part B/Part C end of treatment**

**Table 5: Analysis Visit Window for 12-week follow-up period after Part B/Part C end of treatment**

Visit from SOE	Target Study Day after EOT Visit a	Analysis Window based on Study Day after EOT
12-week Follow-up EOS Visit (Patient not entering Part C)	85 (relative to week 24 visit)	≥2
12-week Follow-up EOS Visit (Patient entering Part C)	85 (relative to week 52 visit)	≥2

**Error! Reference source not found.** Study days are calculated from the day of week 24 visit for patients not entering Part C and the day of week 52 visit for patients entering Part C. Study day = (date of assessment – week 24/52 visit +1) when date of assessment ≥ week 24/52 visit. If patient dose not complete week 24/52 visit, 12-week Follow-up EOS Visit will be not applicable for this patient.

For DSQ data (collected daily by eDiary), the analysis visit windows will be implemented following the procedures below:

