7.4.2. Study Drug Discontinuation

Patients who permanently discontinue from study drug during the double-blind treatment period will be asked to return to the clinic for all remaining study visits for the double-blind treatment period and follow-up period per the visit schedule.

Patients who permanently discontinue from study drug during the extended active treatment period will be asked to return to the clinic for all remaining study visits per the visit schedule.

Patients who permanently discontinue from study drug and who opt to withdraw from the study will be asked to complete an early termination (ET) visit, per [Section 8.1.2](#).

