Study drug accountability		X	X	X	X	X	X	X	X
Concomitant medications/procedures		X	X	X	X	X	X	X	X
Efficacy:²									
DSQ eDiary ⁵	←----- completed daily by patient -----→								
PGIC ⁶					X				X
PGIS ⁶					X				X
EoE Impact Questionnaire ⁷					X				X
EoE Symptom Questionnaire ⁷					X				X
TNSS ⁸					X				X
RQLQ(S)+12 ⁸					X				X
POEM ⁸					X				X
ACQ-5 ⁸					X				X
EoE-EREFS ^{9, 10}									X ^{10, 10a}
Endoscopy with biopsies (histology, IHC, RNA, EndoFLIP) ¹⁰									X ^{10, 10a}
Safety: ^{2, 2a, 14}									
Vital signs ¹¹	X ¹¹	X ¹¹	X	X	X	X	X	X	X
Height ¹²									X
Weight		X	X	X	X				X
Physical examination									X
ECG									X
Adverse events		X	X	X	X	X	X	X	X

	28-Week Extended Active Treatment Period ¹⁴								
Study Procedure	V11 ¹	V12	V13	V14	V15	V16	V17	V18	EOT V19
Week (W)	W24 ¹	W26	W28	W32	W36	W40	W44	W48	W52
Day (D)	D169	D183	D197	D225	D253	D281	D309	D337	D365
Visit Window (Days [d])	+7 d	±7 d	±7 d	±7 d	±7 d	±7 d	±7 d	±7 d	+7 d
Laboratory Testing: ^{2, 2a}									
Hematology, Chemistry					X				X
Pregnancy test ¹³		Urine		Urine	Urine	Urine	Urine	Urine	Urine
Urinalysis					X				X
PK and ADA: ^{2, 2a}									
PK Sample				X					X
ADA sample				X					X
Biomarkers: ^{2, 2a}									
Whole blood RNA (optional)									X
Plasma Eotaxin-3		X		X					X
Serum TARC									X
Serum Total IgE		X		X					X
Allergen-specific IgE, IgG4		X		X					X
Future Biomarker Serum/Plasma		X		X					X

ADA = anti-drug antibody; DSQ = Dysphagia Symptom Questionnaire; ECG = electrocardiogram; EoE-EREFS = Eosinophilic Esophagitis-Endoscopic Reference Score; EOT = end of extended active treatment period; IHC = immunohistochemistry; POEM = Patient-Oriented Eczema Measure; PRO = patient reported outcome; PGA = physician global assessment; PGIC = Patient Global Impression of Change of Dysphagia; PGIS = Patient Global Impression of Severity of Dysphagia; PK = pharmacokinetic; RQLQ(S)+12 = Rhinoconjunctivitis Quality of Life Questionnaire for patients aged 12+ years; TNSS = Total Nasal Symptom Score; V = visit

Table 3: Follow-up Period, Early Termination Visit, and Unscheduled Visit

Study Procedure	12-Week Follow-Up EOS Visit	Early Termination during 12-Week Follow-Up ¹	Early Termination during Parts A, B, or C ¹	Unscheduled Visit before Rescue Treatment	Unscheduled Visit for Other Reasons
Week (W)	12 weeks after EOT visit				
Day (D)	84 days after EOT visit				
Visit Window (Days [d])	±7 d				
Concomitant medications/procedures ¹⁰	X	X	X	X	X
Efficacy:					

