14. If COVID-19 restrictions limit the availability of staff or the patient to have in-clinic visits, the clinic staff should make every effort to contact the patient at the timepoint of the expected in-clinic visit to collect any AEs (including ISRs), any change in concomitant medications and/or procedures, and monthly pregnancy test results, if required.

8.1.1.3. Footnotes for Table 3

1. Patients who are withdrawn from study drug will be asked to complete the 12-week follow-up period and the end of study visit.
2. DSQ eDiary will be completed once daily by the patients after their last meal of the day but before they go to bed. Site personnel should conduct regular checks of patient eDiary compliance.
3. PGIC and PGIS will be completed by the patient via electronic questionnaire at the indicated site visits. See Section 8.2.2.5 and Section 8.2.2.6.
4. EoE Impact Questionnaire and EoE Symptom Questionnaire will be completed by the patient via electronic questionnaire at the indicated site visits. See Section 8.2.2.3 and Section 8.2.2.4.
5. TNSS and RQLQ(S)+12 will be administered only to patients with a documented history of allergic rhinitis; ACQ-5 will be administered only to patients with a documented history of asthma, and only in countries in which a valid translation is available; POEM will be administered only to patients with a documented history of AD. TNSS, POEM, ACQ-5 and RQLQ(S)+12 will be completed via electronic questionnaire and at the indicated site visits. See Section 8.2.2.7, Section 8.2.2.8, Section 8.2.2.9, and Section 8.2.2.10.

6. EoE-EREFS should be completed by the investigator before biopsies for all patients are performed. For Part B enrolled patients, EoE-EREFS will be performed by both the investigators who perform the endoscopies as well as a centralized reading center who will provide EoE-EREFS analysis and scoring from endoscopy imaging. For all endoscopies, the investigators will assess minor esophageal features including mucosal inflammatory and remodeling features.
7. Endoscopy/EoE-EREFS/biopsy procedures should be performed after all other efficacy and safety assessments. The EndoFLIP procedure to measure esophageal distensibility may be performed during the esophagogastroscope procedures at selected North American sites in approximately 150 adult patients.

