##### Part C:

The Part C SAF includes all patients who were randomized in Part B, entered Part C, and received any study drug in Part C. Efficacy, treatment compliance/administration, and all clinical safety data from Part C through a pre-specified cut-off date around the time of Part B completion will be analyzed for Part C SAF patients who entered Part C from Part B.

The actual treatment group as treated for Part B is defined by the following rules:

- For a patient randomized to dupilumab 300 mg QW or dupilumab 300 mg Q2W, if the patient received all placebo injections in Part B, the actual treatment will be assigned as placebo.
- For a patient randomized to dupilumab 300 mg QW or dupilumab 300 mg Q2W, if the patient received at least one dupilumab injections in Part B, the actual treatment will be assigned as the planned treatment.
- For a patient randomized to placebo, if the patient received at least one dupilumab injections in Part B, the actual treatment will be assigned as dupilumab 300 mg Q2W.

The Part B treatment group assignment for analysis of Part C data will be the same as the SAF for Part B.

For safety summaries, the following analysis periods are defined:

- Part B week 24 treatment period is defined as
  - For patients who entered Part C: Day 1 to the date of first dose of Part C study drug (or week 24 visit if patient entered Part C but never received any Part C study drug).

- For patients who did not enter Part C:
  - Day 1 to the week 24 visit if patients completed week 24 visit with known visit date.
  - Day 1 to study day 169 (24 weeks times 7 days/week), or to patient’s last study participation date, whichever comes earlier, if patients did not complete week 24 visit or had missing week 24 visit date.
- Part C extended treatment period for patients who entered Part C is defined as
  - Time after the first dose of study drug in Part C to the date of week 52 visit if patients completed week 52 with known visit date.
  - Time after the first dose of study drug in Part C to study day 365 (52 weeks times 7 days/week), or to patient’s last study participation date, whichever comes earlier, if patients did not complete week 52 visit or had missing week 52 visit date.
- Follow-up period is defined as
  - For patients who entered Part C: the day after the end of Part C extended treatment period to the patient last study participation date.

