  - For patients who did not enter Part C: the day after the end of Part B week 24 treatment period to the patient last study participation date.

The Part B and Part C SAFs will be the basis for the analyses for the Part B treatment period and Part C treatment period, respectively; however, for the analyses for the follow-up period, only a subset of the corresponding SAFs will be included, which is defined as the patients who entered the follow-up period and had at least one visit after week 24 visit (for Part B SAF) and week 52 visit (for Part C SAF).

Due to COVID-19 pandemic, patients are allowed to extend their current assigned dose regimen of study drug (Part B and/or Part C) until endoscopy with biopsy can be performed at week 24 visit and/or week 52 visit. The safety data during the extended dosing period will also be presented in the corresponding analysis period.

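### SAP Table 5 and Section 3.2 leave end-of-study data without a follow-up row for patients who have no week 24 or week 52 visit

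*SAP*

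**What the plan says.** **What is asked of patients.** Footnote 1 to Protocol Table 3 is attached to both early-termination (ET) columns and is repeated in SAP Section 11.2: "Patients who are withdrawn from study drug will be asked to complete the 12-week follow-up period and the end of study visit". Protocol Table 3 places the EOS visit "84 days after EOT visit" and schedules vital signs, weight, hematology, chemistry, urinalysis, PK and ADA there. Protocol 7.4.2 describes a separate route for patients who stop drug but stay in the study: "Patients who permanently discontinue from study drug during the double-blind treatment period will be asked to return to the clinic for all remaining study visits".

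**What the SAP does with the visit.** Table 5 (SAP 6.4) sets the follow-up target day for patients not entering Part C at "85 (relative to week 24 visit"), with week 52 as the anchor for those who entered Part C. If the patient does "not complete week 24/52 visit, 12-week Follow-up EOS Visit will be not applicable for this patient".

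**Other rules that might place the data.** SAP 6.4 states: "Unscheduled visits and early termination (ET) visit will be mapped per the analysis visit windows for Part B and Part C". It has no mapping rule for an EOS visit. The windows after Part B day 190 and Part C day 218 are described as dummy windows for extended dosing.

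**Analysis periods.** SAP 3.2 foresees patients without the anchor visit: "if patients did not complete week 24 visit or had missing week 24 visit date", the Part B period ends at day 169 or last participation, whichever is earlier, and follow-up starts the next day. The same section then limits follow-up-period analyses to "the patients who entered the follow-up period and had at least one visit after week 24 visit (for Part B SAF"), with the matching week 52 condition for Part C.

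**The concern.** Data that the schedule asks for are given no analysis visit. SAP 5.7.2 and 5.7.3 summarize laboratory and vital-sign results by visit, and SAP 5.8 summarizes drug concentration by sampling time. Under Table 5 the follow-up row holds only patients who attended week 24 or week 52.

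Patients who left before that visit plausibly include some who stopped for safety reasons, so their off-drug values 12 weeks later are of interest. The plan collects those values and then has nowhere to show them.

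There is also a possible mismatch in the adverse-event tables. SAP 5.7.1 counts a follow-up TEAE by its onset date but takes the denominator from Section 3.2. A patient with no week 24 visit cannot clearly meet a condition that requires a visit after it. Such a patient could appear in the numerator but not in the denominator.

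**Working it through.** **1. The plan's own figure.** Table 5 defines study day as assessment date − week 24/52 visit date + 1. Protocol Table 3 puts EOS 84 days after end of treatment. So 84 + 1 = 85, which reproduces Table 5's target day.

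**2. A patient without the anchor.** Assume an ET visit on Part B day 113, no week 24 visit, no entry to Part C, and EOS attended 84 days after ET.
- EOS day = 113 + 84 = 197.
- SAP 3.2 ends the Part B period at min(169, 197) = day 169, so days 170 to 197 (197 − 169 = 28 days) count as follow-up.
- Table 5 has no date to count from, so EOS is not applicable.
- Day 197 lies in the Part B window [191, 204], but that window is for extended dosing.
- Counted from the ET visit instead, 197 − 113 + 1 = 85. This meets the Table 5 window (≥2) and equals its target day.

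**3. Earlier terminations.** EOS falls on or before day 190 when ET is on or before 190 − 84 = day 106. With ET on day 85, EOS is on day 169, inside the on-treatment week 24 window. No rule maps an EOS visit there, and doing so would put an off-drug value in an on-treatment row. Section 3.2 also assigns day 169 to the Part B treatment period, leaving 169 − 169 = 0 follow-up days. Table 5 and Section 3.2 therefore both need attention.

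**4. Part C.** On Part C study days, ET on day 134 gives EOS on 134 + 84 = 218, the last day of the week 52 window. ET on day 135 gives 219, the first extended-dosing day. The same gap applies.

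**5. Which outputs depend on the rule.**

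| Output | SAP section | Depends on Table 5? |
|---|---|---|
| Laboratory, vital signs and weight by visit | 5.7.2, 5.7.3 | Yes |
| Drug concentration by sampling time | 5.8 | Yes |
| TEAE assignment by onset date | 5.7.1 | No; the denominator may be affected through 3.2 |
| Counts of potentially clinically significant values | 5.7 | No; counted over treatment and follow-up |
| Patient-level ADA categories | 4.7, 5.9.1 | No |
| ET-visit data | 6.4 | No; mapped by the ET rules |

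**6. Size.** The documents do not say how many patients miss week 24 and still attend EOS. The only related figure is the 15% planning dropout in SAP 2.3. If every such patient missed week 24, 0.15 × 70 = 10.5 per arm, or 3 × 10.5 = 31.5 of 210. With an assumed 5%, the figures are 3.5 and 10.5. These are ceilings at those rates, because not all of these patients would attend EOS.

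**The case against.** The strongest reply is that the group is small and little is lost. Protocol 7.4.2 asks patients who stop drug to keep attending, and those who do so have the anchor visit. The ET visit is for patients who withdraw from the study, and they are the least likely to return 12 weeks later. An abnormality that caused stopping occurs at or before ET, and ET data are mapped. This stands, and it limits the point to descriptive, untested summaries.

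A second reply is that SAP 6.4 summarizes by scheduled visit and applies windows only when scheduled data are unavailable. EOS is a scheduled visit, so a programmer might keep the nominal record. That is possible, but the specific Table 5 footnote says otherwise. Two programmers could reach different results from the same text.

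Three stronger readings are tempting, and the documents support none of them:
- A reader might infer that abnormalities leading to stopping would look less frequent. The incidence outputs do not run through Table 5.
- A reader might infer that the follow-up row is restricted to treatment completers. The condition is attending week 24 or 52, so patients who stopped drug and stayed in the study are included.
- A reader might infer that the SAP discards data the protocol requires. The footnote says only that patients will be asked to complete follow-up.

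**Conclusion.** The gap is real and narrow. For patients who attend EOS without a week 24 or week 52 visit, the SAP gives the EOS laboratory, vital-sign, weight and drug-concentration values no row in the follow-up summaries. The Section 3.2 subset may also drop these patients from follow-up denominators while their TEAEs are counted.

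Efficacy, onset-based TEAE assignment, counts of potentially clinically significant values and patient-level ADA categories are untouched by the Table 5 rule. The number affected is unknown. The figure of 10.5 per arm is a ceiling that assumes the full 15% planning dropout occurs and that all of it misses week 24. A reader might want to turn that into an expected number of lost records, but the documents give no EOS attendance rate from which to do so.

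The change is worth making because the data are already requested and the rule that excludes them is explicit.

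**What to change.** Four changes, made together before database lock:

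1. **Table 5 footnote.** When the week 24/52 visit is missing, count follow-up days from the ET visit, or from last dose + 7 days if there was no ET visit.
2. **Mapping.** Assign the EOS visit of these patients to the 12-week follow-up row, with a flag for early stopping. State that this takes precedence over the Part B and Part C windows.
3. **Section 3.2 follow-up subset.** Replace the condition of a visit after week 24/52 with a visit after the same anchor, so that numerators and denominators match.
4. **Section 3.2 period boundary.** Align the end of the treatment period with the same anchor. Otherwise an EOS visit on day 169 after ET on day 85 is follow-up in Table 5 and treatment period in Section 3.2.

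The cost is SAP text and derivation changes, with no new data. A change to the footnote alone would be incomplete. There are two downsides. The follow-up row pools patients with different treatment durations, which the flag shows. Moving the boundary also reclassifies some days: with ET on day 113, days 114 to 169 (169 − 113 = 56 days) pass from treatment period to follow-up, and TEAEs with onset in those days move with them. The SAP should say so.
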